7.2.3. Tumor Imaging During Treatment

The first imaging assessment should be performed as follows:

- 8 weeks after the first dose of study treatment
- Every 8 weeks (56 days ± 7 days) for 12 months, and then every 12 weeks (± 7 days) thereafter until disease progression is determined or until any of the criteria in Section 7.1.4.2 are met.
- Imaging assessments may be performed more frequently if clinically indicated.

Imaging should follow calendar days and should not be delayed, irrespective of study treatment administration (i.e. delays in cycles or dose holds).

Per RECIST v1.1, responses (PR or CR) should be confirmed by a repeat radiographic assessment. The scan for confirmation of response may be performed no sooner than 4 weeks after the first documented response and no later than the next per-protocol scheduled scan, whichever is clinically indicated.

Radiographic disease assessments should be performed until disease progression per RECIST v1.1, withdrawal of consent, initiation of subsequent anticancer therapy, patient is lost to follow-up, death or defined end of study (see Section 4.5 and Section 6.8).

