7.5.2. Duration of Response

DOR is defined as the time from the date of the first documented response (CR or PR) that is subsequently confirmed, to the earliest date of disease progression, as determined by IRR and investigator per RECIST v1.1, or death due to any cause. If a participant with a CR or PR has neither progressed nor died at the time of the analysis cutoff or at the start of any new anticancer therapy, the participant will be censored at the date of last adequate tumor assessment. The same rules used for censoring of PFS will be applied, see [Section 7.5.5](#) for more details. DOR will be calculated for participants who have achieved a confirmed response (i.e., CR or PR).

An estimate of the DOR survival function will be constructed using the KM method (Kaplan & Meier, 1958³) as implemented in PROC LIFETEST. The 25%, median, and 75% DOR (in months) will be summarized along with 95% confidence intervals as calculated from the PROC LIFETEST output (using method of [Brookmeyer & Crowley, 1982¹]).

Frequency distribution (<3 months, ≥3 months, ≥6 months, ≥9 months, ≥12 months, ≥24 months) will be provided.

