7.5.5. Progression-free Survival

Progression-free survival is defined as the time from the date of first dose of study drug to the earliest date of disease progression, as determined by IRR and investigator per RECIST v1.1, or death due to any cause, whichever occurs first, and will be summarized in months:

$$\text{PFS (months)} = [(\text{date of event or censoring} - \text{date of first dose}) + 1] / 30.4375.$$

Participants without an event or with an event more than 16 weeks (for the first 12 months after treatment start date) or 24 weeks (after the first 12 months of treatment start date) after the last adequate tumor assessment will be censored on the date of the last adequate tumor assessment that documented no progression. In addition, if a new anticancer therapy is started prior to an event, the participant will be censored on the date of the last adequate tumor assessment that documented no progression prior to the start of the new anticancer therapy. Note: if date of progression occurs on the same date as the start of new anticancer therapy, the progression will be counted as an event.

An adequate post-baseline assessment is defined as an assessment where a response of CR, PR, SD, non-CR/non-PD, or PD can be determined. Time points where the response is NE or no assessment was performed will not be used for determining the censoring date.

Participants with no baseline tumor assessment (including participants with an inadequate baseline assessment) or with no adequate post-baseline tumor assessments within 16 weeks after treatment start date will be censored on the day of treatment start date, unless the participant dies within 16 weeks of treatment start date, in which case, death will be an event on date of death.

The censoring and event date options to be considered for the PFS analysis are presented in Table 4.

Table 4. PFS Outcome and Event Dates

Situation	Date of Progression/Censoring	Outcome
No adequate baseline assessment	Date of treatment start date ^a	Censored ^a
PD or death ≤ 16 (or 24) ^b weeks after last adequate tumor assessment or ≤ 16 weeks after treatment start date	Date of PD or death	Event
PD or death > 16 (or 24) ^b weeks after the last adequate tumor assessment ^c	Date of last adequate tumor assessment ^c documenting no PD prior to new anticancer therapy or missed assessments	Censored
No PD		
New anticancer therapy given		

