^a If the participant dies ≤ 16 weeks after treatment start date, the death is an event with date on death date.

^b Durations are equal to 2 times the length of the tumor assessment interval, which is 16 weeks for the first 12 months after treatment start date, and 24 weeks thereafter.

^c If there are no adequate post-baseline assessments prior to the PD or death, then the time without adequate assessment should be measured from treatment start date; if the criteria is met, the censoring will be on treatment start date.

An estimate of the PFS survival function will be constructed using the KM method (Kaplan & Meier, 1958³) as implemented in PROC LIFETEST. The 25%, median, and 75% DOR (in months) will be summarized along with 95% confidence intervals as calculated from the PROC LIFETEST output (using method of [Brookmeyer & Crowley, 1982¹]).

Frequency counts and percentages of participants with each event type (PD or death) and censoring reasons will be summarized. Censoring reasons are as follows:

- Ongoing in the study without an event
- No adequate baseline assessment
- No adequate post-baseline assessment
- New anticancer therapy was given
- Progression or death after 2 or more missed assessments
- Withdrawal of consent
- Lost to follow-up

If a participant meets multiple definitions for censoring the list below will be used to define the hierarchy.

Table 5. Censoring Reasons and Hierarchy

Hierarchy	Condition	Censoring Reason
1	No adequate baseline assessment	No adequate baseline assessment
2	Start of new anticancer therapy before event.	Start of new anticancer therapy
3	Event after 2 or more missing or inadequate postbaseline tumor assessment	Event after missing or inadequate assessments ^a
4	No event and [withdrawal of consent date \geq , date of first dose OR End of study (EOS) = Participant refused further follow-up]	Withdrawal of consent
5	No event and lost to follow-up in any disposition page	Lost to follow-up
6	No event and [EOS present OR any disposition page after screening says participant will not continue into any subsequent phase of the study] and no adequate postbaseline tumor assessment	No adequate postbaseline tumor assessment
7	No event and none of the conditions in the prior hierarchy are met	Ongoing without an event

a .More than 16 weeks after last adequate tumor assessment.

A graph of the estimated KM curve will be presented.

In addition, time to progression/censoring, event and censoring reasons will be listed.

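### SAP Table 5 footnote a gives a flat 16-week missed-scan limit, while the PFS text and Table 4 allow 24 weeks after month 12 and row 3 itself requires two missed scans

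*SAP*

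**What the plan says.** **Scan schedule.** Protocol 7.2.3 schedules imaging every 8 weeks "for 12 months, and then every 12 weeks", each with a 7-day window either side.

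**PFS limit.** The body text of SAP 7.5.5 censors participants "with an event more than 16 weeks (for the first 12 months after treatment start date) or 24 weeks (after the first 12 months" from treatment start). The Table 4 row for late events reads "PD or death > 16 (or 24") weeks. Footnote b gives the principle: "Durations are equal to 2 times the length of the tumor assessment interval, which is 16 weeks for the first 12 months", "and 24 weeks thereafter". The censoring date is the last adequate assessment that showed no progression.

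**Censoring reasons.** Table 5 ranks the reasons for participants who qualify for more than one. Row 3 covers an event that follows at least two missing or inadequate post-baseline assessments. Its reason label carries footnote a: "More than 16 weeks after last adequate tumor assessment". The footnote has no 24-week alternative.

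**DOR.** SAP 7.5.2 states: "The same rules used for censoring of PFS will be applied".

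**The concern.** Footnote a puts a number on a condition that the rest of the section defines differently after month 12. If it is coded as written, a late progression that the governing rule counts as an event would be censored, and its time moved back to the last scan by up to 24 weeks. If event status is coded from Table 4 and the reason from footnote a, the same participant would be an event that also carries a censoring reason, although SAP 7.5.5 tabulates and lists both.

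The cases lie in the late part of the PFS and DOR curves. Dropping late events there raises the curve, so the error would flatter durability. Follow-up does reach this period: the final ORR analysis for treatment-naïve participants comes 14 months after the last of them is enrolled (SAP 7.5), DOR is also tabulated at 12 and 24 months or more (SAP 7.5.2), and the study may run until 2 years after the last patient starts treatment (Protocol 4.5).

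**Working it through.** **1. Reproduce the plan's limit.** Limit = 2 × scan interval, with the intervals from Protocol 7.2.3.

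- First 12 months: 2 × 8 = 16 weeks.
- Thereafter: 2 × 12 = 24 weeks.

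Both agree with Table 4 footnote b. The flat 16 weeks in Table 5 footnote a agrees only for the first 12 months. Later it is 16/12 = 1.33 intervals, which is less than two.

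**2. Classify example cases.** PD or death is an event if gap ≤ limit, otherwise censored. Here the 16- or 24-week period is judged at the event date.

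| Last adequate scan (week) | PD or death (week) | Gap (weeks) | Text, Table 4, footnote b | Footnote a alone |
|---|---|---|---|---|
| 24 | 40 | 16 | event | event |
| 24 | 42 | 18 | censored | censored |
| 60 | 72 | 12 | event | event |
| 60 | 78 | 18 | event | censored |
| 60 | 80 | 20 | event | censored |
| 60 | 84 | 24 | event | censored |
| 60 | 85 | 25 | censored | censored |

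The two disagree only for PD or death after month 12 with a gap above 16 and up to 24 weeks.

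**3. Compare footnote a with its own row.** Take week 60 adequate, week 72 missed, PD at week 84. One scan is missed, so row 3's condition of two or more is not met. The gap is 84 − 60 = 24 weeks, which is above 16, so footnote a is met. The row and its footnote therefore give different answers. With no missed scan the nominal gap is 12 weeks, or at most 14 with both 7-day windows used, so the footnote has no effect.

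**4. Size (illustrative).** The documents give no missed-scan rate, so this step rests on assumptions: 60 participants, exponential PFS, scans missed at random, 15% of events being deaths, follow-up uniform from 60 to 130 weeks, and scans at weeks 8 to 48 and then every 12 weeks from week 60. Each row is 400 simulated trials. The medians 10.9 and 14.9 months are PFS figures quoted in Protocol 2.1.2 and 2.3; 24 months is an assumption. The footnote is applied on the gap alone, ignoring row 3's condition, so this is the case in which the footnote is fully programmed.

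| True median (months) | Scans missed | Mean events, Table 4 rule | Mean events lost under footnote a | Typical KM median, Table 4 → footnote a (months) |
|---|---|---|---|---|
| 10.9 | 5% | 43.0 | 1.03 | 11.0 → 11.0 |
| 10.9 | 10% | 42.2 | 2.00 | 11.0 → 11.0 |
| 10.9 | 20% | 39.6 | 2.82 | 13.8 → 13.8 |
| 14.9 | 5% | 36.4 | 1.00 | 16.6 → 16.6 |
| 14.9 | 10% | 35.5 | 1.71 | 16.6 → 16.6 |
| 14.9 | 20% | 33.3 | 2.84 | 16.6 → 16.6 |
| 24 | 5% | 26.4 | 0.84 | 22.1 → 22.1 |
| 24 | 10% | 26.0 | 1.36 | 22.1 → 22.1 |
| 24 | 20% | 24.2 | 2.28 | 22.1 → 24.8 |

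With a true median of 24 months, the share of trials in which the KM median was not reached rose by 7, 10 and 21 percentage points at 5%, 10% and 20% missed. With 14.9 months the rise was at most 3 points, and with 10.9 months it was zero.

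**5. After the correction.** If footnote a carries the 16/24 limit, the two columns in step 2 agree for every gap.

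**The case against.** The best defense is that Table 5 does not decide event status. SAP 7.5.5 assigns the event and censoring dates to Table 4, which has the date and outcome columns. Table 5 has neither and serves to label and rank reasons. The body text, Table 4 and footnote b agree with one another and state the principle, so a careful programmer would read footnote a as an omission. PFS and DOR are secondary endpoints with descriptive Kaplan-Meier estimates and no test.

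Most of this stands, and it rules out three stronger readings that a reader might infer.

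- *The SAP has two rival PFS derivations of equal standing.* It does not: PFS cannot be derived from Table 5, which gives no censoring date.
- *Table 5 censors every progression found after a single missed late scan.* It does not on its own terms, because one missed scan fails row 3's condition. Only the footnote, read without its row, would do so.
- *The plan leaves open which date decides between 16 and 24 weeks.* Take week 48 (day 336) adequate, week 60 (day 420) missed and PD at week 72 (day 504), a gap of 24 weeks. Judged at the scan date this is censored; judged at the event date it is an event. But the wording of SAP 7.5.5 attaches the period to the event, and the 12-week interval already applies, so footnote b also points to 24 weeks. A clarifying line would help, but the two readings are not equally supported.

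What the defense does not remove is the footnote itself. It states a numeric limit that is wrong after month 12 by the SAP's own principle. SAP 7.5.5 describes the Table 5 entries as definitions for censoring. Rows 4 to 7 each require that there be no event, whereas row 3 presupposes one, so code written from this table could censor an actual event.

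**Conclusion.** The inconsistency is real and narrow. After month 12, Table 5 footnote a conflicts with the PFS text, with Table 4 and its footnote b, and with row 3's own condition. It matters only if the footnote is programmed, and then only for PD or death more than 16 and up to 24 weeks after the last adequate scan, in PFS and DOR by IRR and by investigator.

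Under the assumptions in the working, about 1 to 3 events per 60 participants change status. The typical Kaplan-Meier median was unchanged in eight of the nine settings; it moved, from 22.1 to 24.8 months, only with a true median of 24 months and 20% of scans missed. The missed-scan rates are assumed, and DOR was not simulated separately.

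A reader might take the share of participants still event-free at month 12 as the share affected. With the comparator medians in Protocol 2.1.2 that share would be 0.5^(12/10.2) = 44% to 0.5^(12/10.9) = 47%. Those participants are at risk of a late event; few would have one after a gap of the relevant length. Primary ORR, its exact test and the sample size do not use this limit and are not affected.

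**What to change.** Replace footnote a to Table 5 with: *More than 16 weeks (during the first 12 months from treatment start) or more than 24 weeks (later) since the last adequate assessment; see Table 4 footnote b.* State that this applies to DOR as well as PFS.

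Optionally, add one sentence to SAP 7.5.5 saying that the period is judged at the date of PD or death, as the present wording suggests.

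The cost is one or two lines in the SAP, with no new data and no change to the primary analysis. It is best done before the late PFS and DOR data are analyzed, so that the choice does not have to be made with results in view.

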7.5.6. Overall Survival

OS is defined as the time from the date of first dose of study treatment to the date of death due to any cause. If a death has not been observed by the date of the analysis cutoff, OS will be censored at the date of last contact, unless death or last contact date occurs after the data cutoff date in which case OS will be censored at the data cutoff date.

The survival distribution function for OS will be estimated using the KM method as described for PFS in [Section 7.5.5](#). A graph of the estimated KM curve will be presented.

Frequency counts and percentages of participants with an event (death) and censoring reasons will be summarized. Censoring reasons are as follows:

- Ongoing and no death
- Withdrawal of consent
- Lost to follow-up

- No longer follow for survival (alive participant who discontinued from the study for reason different from withdrawal consent and lost to follow-up).

7.6. Safety Analysis

All safety analyses will be performed using the appropriate data for all participants in the SS unless otherwise stated.

7.6.1. Extent of Study Drug Exposure

Duration of exposure will be evaluated separately for encorafenib and binimetinib. It is defined as (date of last (non-zero) dose of study drug – date of first dose of study drug) + 1 and will be summarized in months including descriptive statistics (n, mean, standard deviation, median, minimum, maximum) and a frequency distribution (≤ 1 month, >1 to ≤ 3 months, > 3 to ≤ 6 months, >6 to ≤ 12 months, >12 to ≤ 24 months, > 24 months).

Cumulative dose is defined as:

- **Actual cumulative dose** (mg) = sum of all actual doses taken during the dosing period

For participants who did not take any drug the actual cumulative dose is by definition equal to zero.

Dose intensity and relative dose intensity are defined as follows:

- **Actual dose intensity** (mg/day) = actual cumulative dose (mg) / [duration of exposure (days)]
- **Relative dose intensity** = $100 \times [\text{actual dose intensity (mg/day)} / \text{intended dose intensity (mg/day)}]$

A summary of exposure, including duration, cumulative dose, actual dose intensity, and relative dose intensity (including categories $<50\%$, $50\%<75\%$, $75\%<90\%$, $90\%<110\%$, and $\geq 110\%$, if applicable), will be presented for each study drug. Duration of exposure, cumulative dose, actual dose intensity, and relative dose intensity will also be listed for each participant.

7.6.1.1. Dose Modifications

Dose reduction:

Dose reductions are permitted for both encorafenib and binimetinib and will be summarized based on the dose modification data collected on the respective study treatment eCRF page.

Dosing interruption:

A dosing interruption will be indicated in the study treatment eCRF by a dosing record with a total daily dose of 0 mg for one or more days.

Dosing interruption will be summarized based on the dose modification data collected on the eCRF page. However, in order not to over count interruptions, dosing records with 0 mg entered as last dosing record will not be counted as interruptions. Those represent the reason for permanent discontinuation and will therefore be presented in the reason for treatment discontinuation analysis.

Frequency counts and percentages of participants who have dose reductions or any study drug interruptions, and the corresponding reasons, will be provided. The number of dosing interruptions per participant, and the duration of dosing interruptions (days) will also be summarized for each study drug.

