6.6. Dose Modification

6.6.1. Dose Interruptions

Following initiation of therapy, treatment with encorafenib and binimetinib may be delayed to allow resolution of toxicity. Patients may resume treatment if no medical condition or other circumstance exists that, in the opinion of the Investigator, would make the patient unsuitable for further participation in the study.

Individual decisions regarding dose interruptions and modifications should be made using appropriate clinical judgment, considering relatedness of the AE to the study treatment and the patient's underlying condition. Adverse events that have a clear alternative explanation, or transient (\leq 72 hours) abnormal laboratory values without associated clinically significant signs or symptoms may be exempt from dose-reduction rules. The treating Investigator

should refer to and follow the labeled guidance and/or institutional guidelines for the management of toxicities relating to encorafenib and binimetinib. Detailed guidelines can also be found in Appendix 2 and Appendix 3.

Dose interruptions are permitted in the case of medical/surgical events or logistical reasons not related to study treatment (e.g., elective surgery, unrelated medical events, vacation, holidays). Patients should be placed back on study treatment within 2 weeks (14 days) of the scheduled interruption, unless otherwise discussed with the Sponsor. The reason for interruption will be documented in the patient's study record.

If a patient misses > 6 weeks (i.e., 42 consecutive days) of dosing with encorafenib, study treatment with encorafenib will be permanently discontinued. Due to the potential for limited efficacy of binimetinib alone in the study population, if a patient permanently discontinues treatment with encorafenib, they must also permanently discontinue treatment with binimetinib.

If a patient misses > 6 weeks (i.e., 42 consecutive days) of dosing with binimetinib, study treatment with binimetinib will be permanently discontinued. If a patient discontinues treatment with binimetinib, the patient may continue treatment with encorafenib. Due to the potential for increased toxicity when binimetinib is discontinued, doses of single-agent encorafenib may need to be decreased.

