7.1.9. Reporting Conventions

Unless specified otherwise, durations of events (e.g., duration of treatment) will be calculated in days as (stop date – start date + 1).

The following conversion factors will be used to convert days into weeks, months or years:

$$1 \text{ week} = 7 \text{ days}, 1 \text{ month} = 30.4375 \text{ days}, 1 \text{ year} = 365.25 \text{ days}.$$

Demographics and physical measurements:

- Age (years):
 - (date of given informed consent - date of birth + 1) / 365.25
 - In case of only year and month given: (year/month of given informed consent – year/month of birth)
 - In case only year of birth is given: (year of given informed consent – year of birth)
 - The integer part of the calculated age will be used for reporting purposes.

For each analysis, a data cutoff date will be determined. Only data with an assessment/finding dates (eg, vital sign assessment date, tumor scan date, laboratory collection date, etc) or event/intervention start date (eg, AE start date, concomitant medication start date) before or on the cutoff date will be included in the analysis.

All events with a start date before or on the cutoff date and an end date after the cutoff date will be considered as continuing at the cutoff date. The same rule will be applied to events starting before or on the cutoff date and not having a documented end date. Participants with a last contact date or a date of death after the data cutoff date will be considered alive at the data cutoff date. Participants known to be on treatment or discontinued the treatment after the cutoff date will be considered on treatment at the time of data cutoff date.

In general, missing values will be handled as follows unless otherwise specified. For continuous variables at baseline, missing values will be excluded from calculation of summary statistics, and the number and percent of participants with missing values will be displayed. For categorical values at baseline, the number and percent of participants with a missing value will be displayed. For missing post-baseline values, the method for reporting missing values will depend on the summary table.

Qualitative/categorical data will be summarized by frequency counts and percentages. Percentages will be calculated using the number of participants or subgroup as the denominator. Continuous data will be summarized using appropriate descriptive statistics (e.g. mean, standard deviation, median, minimum, and maximum).

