7.2. Participant Disposition

Participant disposition analyses will use the SS unless otherwise stated.

The following disposition categories will be summarized:

- Number (%) of participants who received at least one dose of study treatment
- Number (%) of participants who are still on treatment
- Number (%) of participants who discontinued the treatment
- Primary reasons for treatment discontinuation
- Number (%) of participants who discontinued the treatment but are still in follow-up for disease or for survival
- Number (%) of participants who discontinued the study
- Primary reasons for study discontinuation

Inclusion and exclusion criteria for each of the analysis sets will also be summarized.

Participant disposition data will also be listed.

Screen failure participants are those who were screened, but never started the study treatment for any reason. The data collected on these participants will not be included in any analyses. A listing of reasons for screen failure will be presented.

A separate listing will describe each participant's inclusion or exclusion status for each of the analysis sets defined in [Section 5](#).

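### SAP 7.6.1.1 treats every final 0 mg record as permanent discontinuation, so a dose hold still open at the data cutoff is lost from the interruption summaries or mislabelled as a discontinuation

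*SAP*

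**What the plan says.** SAP 7.6.1.1 sets out how a hold is recorded: "A dosing interruption will be indicated in the study treatment eCRF by a dosing record with a total daily dose of 0 mg". A single day is enough. To avoid over-counting, it then says that "dosing records with 0 mg entered as last dosing record will not be counted as interruptions". The reason follows: "Those represent the reason for permanent discontinuation and will therefore be presented in the reason for treatment discontinuation analysis". The rule does not require an end-of-treatment page or a recorded decision to stop the drug, and it makes no exception for participants who have not stopped by the cutoff.

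Three other places bear on such participants:

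- SAP 7.1.9 limits each analysis to records whose start date falls "before or on the cutoff date will be included in the analysis". On status it says: "Participants known to be on treatment or discontinued the treatment after the cutoff date will be considered on treatment".
- SAP 7.2 gives these participants their own disposition line: "Number (%) of participants who are still on treatment".
- Protocol 6.6.1 says when a hold turns into a discontinuation: "If a patient misses > 6 weeks (i.e., 42 consecutive days) of dosing with binimetinib, study treatment with binimetinib will be permanently discontinued". It has the same limit for encorafenib.

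**The concern.** The exclusion is sound for someone who has stopped the drug. It is applied, however, to every final 0 mg record, and at a cutoff with participants still on treatment some of those records can be temporary holds.

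What is at stake is the all-cause description of dose interruptions. SAP 7.6.1.1 is where the plan reports how many participants had an interruption, the reasons, the number per participant and the duration in days, for each drug. An open hold is missing from all four. If a programmer instead follows the second sentence of the rule literally, the hold becomes a discontinuation for someone whom SAP 7.1.9 and 7.2 count as on treatment. The two tables would then disagree.

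**Working it through.** The plan states no figure for this rule, so there is none to reproduce. The check has three steps.

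**1. Can an open hold be the last included record of a participant who has not discontinued?** Yes.

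- SAP 7.1.9 drops records that start after the cutoff. A hold that spans the cutoff is then the last record, even if dosing resumed later.
- Protocol 6.6.1 does not make that hold a discontinuation until more than 42 consecutive days have been missed.
- Participants may well be on treatment at the relevant cutoffs. SAP 7.5 sets the final ORR analysis for treatment-naïve participants at 14 months after the last of them enrols. Protocol 4.5 lets the study run to 2 years after the last patient starts, and protocol Table 2 foresees patients still being treated even then.

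**2. What does the rule do to such a record?** Four invented dosing histories at constant full dose, with the cutoff at day 100, were run through the rule as written. They were run again with the exclusion limited to documented discontinuations.

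| History | As written | Restricted rule |
|---|---|---|
| Hold days 41-50, then dosing to day 100 | 1 interruption, 10 days | 1 interruption, 10 days |
| Dosed days 1-80, hold open from day 81 | 0 interruptions, 0 days | 1 interruption, 20 days |
| Dosed days 1-80, hold days 81-109, resumed day 110 | 0 interruptions, 0 days | 1 interruption, 20 days |
| Dosed days 1-80, discontinued, final 0 mg record on day 81 | 0 interruptions | 0 interruptions |

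The 20 days are 100 − 81 + 1. Only the two open holds change. The resolved hold and the true discontinuation come out the same under both rules, so the aim of not over-counting is kept.

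**3. How many participants?** The documents do not say. SAP 4.3 gives at least 60 + 37 = 97 treated participants and does not expect more than 107. Assume that 20-60% are on treatment at the cutoff and that 2-10% of those are on hold that day:

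- Low end: 97 × 0.20 × 0.02 = 0.4.
- Middle: 97 × 0.40 × 0.05 = 1.9; 107 × 0.40 × 0.05 = 2.1.
- High end: 107 × 0.60 × 0.10 = 6.4.

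These figures count participants with an open hold. Fewer would move from not interrupted to interrupted, because anyone with an earlier resolved hold is already counted.

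**The case against.** The strongest reply is that the intent is clear. The rule exists to prevent over-counting, it describes the records it means as permanent discontinuations, and SAP 7.1.9 treats events without an end date as continuing at the cutoff. A sensible programmer might keep an open hold. The SAP is also to be read with the eCRF, which is not available here and may separate temporary holds from permanent stops. This lowers the chance of an actual error. It does not repair the text, because the specific exclusion in 7.6.1.1 removes the record before its continuing status can matter.

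Three stronger readings are tempting, and the documents do not support them:

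- *The participant is reported as never interrupted.* Not in general. SAP 7.6.4 separately tabulates adverse events that led to interruption, overall and by drug, and the last-record exclusion is not stated there. An AE-driven open hold can still appear. Holds for other reasons, such as the elective surgery or vacation allowed by protocol 6.6.1, have no such second route.
- *The error always favours the regimen.* That would hold only if the open hold appeared in neither table. Read literally, 7.6.1.1 sends it to the discontinuation reasons, which is unfavourable. The direction is not fixed.
- *The rule inflates relative dose intensity.* Rule 7.6.1.1 does not enter that calculation. SAP 7.6.1 ends exposure at the "date of last (non-zero) dose of study drug". In the two open-hold histories, relative dose intensity is 80/80 = 100% under either interruption rule, against 80/100 = 80% if measured to the cutoff. Ending exposure at the last dose taken is a defensible choice, and changing it is a separate, debatable question.

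The interim analysis also adds little. SAP 7.8 specifies only a response criterion for it, and SAP Table 1 shows that this version was written after the first interim.

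**Conclusion.** The rule is wrong as written for any hold in progress at a data cutoff. The hold is either lost from the count, reasons, number and duration in SAP 7.6.1.1, or listed as a discontinuation in contradiction of SAP 7.1.9. No other passage returns it to those summaries.

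The consequence is probably small: about 0.4 to 6.4 open holds per cutoff, on assumed proportions that the documents neither give nor exclude. It is confined to descriptive safety tables. The primary ORR analysis is not affected. The conclusion rests on reading 7.6.1.1 as it stands and on taking the last record to be the last one included under the cutoff rule. If it meant the last record in the whole database, only holds still open at data extraction would be misclassified.

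**What to change.** In SAP 7.6.1.1, exclude a final 0 mg record from the interruption summaries only if permanent discontinuation of that drug is documented on or before the cutoff. Otherwise count it as an interruption ongoing at cutoff, with its reason, and measure its duration to the cutoff date.

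The condition should be set for each drug separately, because protocol 6.6.1 allows encorafenib to continue after binimetinib has been stopped. SAP 7.1.11 already uses a similar test for a missing last-dose date: with neither an end-of-treatment page nor a death date, the participant is treated as ongoing.

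The cost is about two sentences and one programming condition, with no new analysis. Reported interruption counts may rise slightly. The dose-intensity definition in SAP 7.6.1 can stay as it is.
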